The time-to-event variables will be analysed using the Cox proportional hazards model, including randomisation arm, age (as a continuous variable), severity at inclusion, and centre as model terms. The hazard ratio between the arms will be presented with the 95% CI and p-value of the model. Kaplan-Meier curves will be presented by the arm for each appropriate endpoint.

For the primary objective, both overall and by subgroups, the following statistics will be provided: effect size, confidence intervals, number needed to treat and absolute risk reduction as appropriate.

All tests will be two-sided with a unilateral significance level of 0.025% adjusted for the interim analysis.

Subgroup analyses

Subgroup analyses will be performed to assess the consistency of the treatment effect between subgroups without multiplicity adjustment. The following subgroups will be assessed for the primary endpoint:

- Fisher grade I to III versus IV
- Age: <50 years; >=50 and <=70 years; >70 years

The treatment effect for the total population and subgroups will be represented using forest plot graphs.

For HR and OR in subgroup analyses, the significance of the interaction will be tested using the method proposed by Altman & Bland 2003.

Treatment of missing data

For the analysis of the primary endpoint, in the event of study exit prior to evaluation of the primary endpoint (6 months), the last recorded mRS value will be used (LOCF method, mRS at ICU discharge) patients will be considered as non responders if no mRS are recorded.

For all other variables, in case of a significant proportion of missing data (>10% of subjects), a sensitivity analysis using multiple conditional imputation techniques by chained equations (MICE) will be performed, according to a conservative principle, using the mean severity at inclusion as the central position parameter and an estimate of the intra-patient variability in the placebo group as the dispersion parameter. Sensitivity analysis based on imputed data will be considered secondary.

Further details on the treatment of missing data will be provided in the SAP.

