12.2.1 Primary Estimand – Intention-to-Treat (ITT) Analysis

This estimand aims to assess the effect of cilostazol added to nimodipine on the modified Rankin Scale (mRS) at 6 months, considering all randomized patients, regardless of intercurrent events.

- Target Population: All randomized patients.
- Variable of Interest: mRS at 6 months, dichotomized as favorable outcome (mRS 0-2) vs. unfavorable outcome (mRS 3-6).
- Handling of Intercurrent Events:
 - Early treatment discontinuation → "Treatment Policy" strategy: Patients remain in their randomized group, regardless of treatment adherence.
 - Death before 6 months → "Composite" strategy:
 - Neurological death → Counted as mRS=6.
 - Non-neurological death → Counted as mRS in ITT analysis and a secondary analysis excluding these patients.
 - Loss to follow-up → "Composite" strategy: Last observation carried forward (LOCF) with multiple imputation as a sensitivity analysis.
- Estimation Method: Logistic regression adjusted for age and initial severity (GCS grade) and centre.

◆ Justification: This approach respects the ITT principle, ensures comparability between groups, and provides a realistic assessment of treatment effect.

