12.2.2 Secondary Estimand – Per-Protocol (PP) Analysis

This estimand aims to measure the effect of cilostazol only in patients who completed the treatment without interruption.

- Target Population: Patients who received at least 80% of prescribed doses over the 14-day treatment period.
- Variable of Interest: mRS at 6 months (favorable vs. unfavorable) otherwise LOCF.
- Handling of Intercurrent Events:
 - Early treatment discontinuation → "Principal Stratum" strategy: Only patients who completed treatment are analyzed.
 - Death before 6 months → "Composite" strategy (mRS=6 if neurological, secondary analysis excluding non-neurological deaths).
- Estimation Method: Logistic regression model restricted to patients who completed treatment.

◆ Justification: This analysis assesses the specific effect of cilostazol without treatment adherence interference.

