12.3 Management of Intercurrent Events – Methodological Approach

In this trial, we do not anticipate the use of rescue therapy, nor the occurrence of an intercurrent event directly related to the drug. The selected strategies reflect this specificity.

Intercurrent Event	Strategy for ITT Estimand	Strategy for PP Estimand	Justification
Early treatment discontinuation	"Treatment Policy" – Analyze in randomized group	"Principal Stratum" – Exclude	Maintains comparability in ITT, assesses adherence in PP.
Neurological death	"Composite" – Counted as mRS=6	"Composite" – Counted as mRS=6	Maintains comparability between groups.
Non-neurological death	"Composite" Sensitivity analysis	"Composite" Sensitivity analysis	Excludes deaths unrelated to the study in a secondary analysis.
Loss to follow-up before 6 months	"Composite" – LOCF + Multiple Imputation	"Composite" – LOCF + Multiple Imputation	Reduces bias due to missing data.

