Stage	Information proportion	Beta spent this stage	Cumulative beta spent	Percentage beta spent at this stage	Cumulative percentage
1	0.33	0.0264	0.0264	13.2	13.2
2	0.67	0.0901	0.1165	45.7	58.3
3	1.00	0.0835	0.2000	41.7	100.0

Boundary Probabilities for $\delta = -0.11$

Number of Simulations: 100000

Futility Boundaries: Binding

After Efficacy Boundary Crossing: Hold Out

After Binding Futility Boundary Crossing: Hold Out

 Alternative Hypothesis: $P1 - P2 < 0$ (one-sided)

P1: 0.65

P2: 0.76

 δ : -0.11

Stage	N1	N2	Efficacy		Futility	
			Boundary	Probability	Boundary	Probability
1	95	95	-3.7103	0.0253	0.2701	0.0277
2	189	189	-2.5111	0.4166	-1.1224	0.0885
3	284	284	-1.9308	0.3597	-1.9308	0.0821

Average N1: 226.

Average N2: 226

[figure not shown]

Figure 1.

12.6 Specify if subjects who leave the research prematurely will be replaced and in what proportion.

The primary outcome is assessed only one time 6 months after Day 0 (5 months and a half after last day of treatment) that could lead to patient's loss to follow up. Nevertheless, SAH is a serious condition that requires a long and close patient's monitoring. That will limit patient's loss to follow up. The patients who leave study prematurely (for loss to follow up or death) won't be replaced and will be considered as non responder patients in the main analysis of primary criterion.

Some sensitivity analyses will be performed with complete cases only.

Only, the particular circumstance of patient resignation will lead to exit patient of the primary analysis. A 10% rate of non evaluable patients is foreseen.

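### The protocol gives two incompatible primary rules for a patient lost before the 6-month mRS: carry the ICU-discharge mRS forward (12.1, 12.2.1, 12.3) or score as non-responder (12.6)

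*Protocol*

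**What the plan says.** All references are to the protocol.

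- **12.1, treatment of missing data.** If a patient exits before the 6-month assessment, "the last recorded mRS value will be used (LOCF method, mRS at ICU discharge". As a fallback, "patients will be considered as non responders if no mRS are recorded".
- **12.2.1, primary (ITT) estimand.** For loss to follow-up: "Last observation carried forward (LOCF) with multiple imputation as a sensitivity analysis".
- **12.2.2, per-protocol estimand.** "mRS at 6 months (favorable vs. unfavorable) otherwise LOCF". This supports the LOCF reading but is not the main analysis.
- **12.3, table of intercurrent events.** "LOCF + Multiple Imputation" for both estimands, without saying which of the two is primary.
- **5.2.** An mRS at ICU discharge is collected by a blinded technician expressly to cover loss to follow-up.
- **12.6.** Patients who leave early through loss to follow-up or death "will be considered as non responder patients in the main analysis of primary criterion". There is no LOCF step.

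On the analysis set, 12.1 and 12.2.1 take all randomised patients, whereas 12.6 says that "the particular circumstance of patient resignation will lead to exit patient of the primary analysis". Section 5.8.1.2 bars use of data after consent is withdrawn unless the patient agrees in writing.

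**The concern.** A patient discharged from ICU with an mRS of 0-2 and then lost is a responder under 12.1 and 12.2.1 and a non-responder under 12.6. Each text presents its rule as primary, so the primary result depends on which section the analyst follows. If this is left open until outcomes are known, the choice can move the final z across the 1.9308 limit. Section 12.1 leaves further detail on missing data to the SAP, but a SAP that follows either rule departs from the other section.

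**Working it through.** **Where the rules differ**

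| Lost or dead before 6 months | 12.1 / 12.2.1 | 12.6 |
|---|---|---|
| Death (mRS 6) | non-responder | non-responder |
| Lost, ICU-discharge mRS 3-5 | non-responder | non-responder |
| Lost, no mRS recorded | non-responder | non-responder |
| Lost, ICU-discharge mRS 0-2 | **responder** | **non-responder** |

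**Inputs from the protocol (12.5).** Favourable rates 0.65 and 0.76; one-sided alpha 0.025; 284 per arm, raised to 315 for drop-out of up to 10%; looks at 95, 189 and 284 per arm. With signs reversed, the efficacy limits are 3.7103, 2.5111 and 1.9308, and the binding futility limits at the two interims are -0.2701 and 1.1224. The second futility limit is taken from the boundary table; 12.7 prints it differently.

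**Assumptions.** Loss of 2, 5 or 10% per arm (6, 16 or 31 of 315); unadjusted pooled z; interims on completers, as 12.5 and 12.7 describe; ICU-discharge favourable rates among lost patients as given below, because the protocol states none.

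**The plan's own figure.** Simulation at 95/189/284 (400,000 trials) gives power 0.800 against the stated 0.8016, and alpha 0.025. The inflation 284/0.9 = 315.6 agrees with the stated 315 to within one patient.

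**The conclusion can change.** z = (p2 - p1) / sqrt(2p(1 - p)/n), with p the pooled rate. Take 184/284 against 207/284 favourable, with 31 lost per arm.
- 12.6: 184/315 against 207/315; p = 391/630 = 0.621; z = 0.0730/0.0387 = 1.89, which misses 1.9308.
- LOCF with 15 of the 31 favourable in each arm: 199/315 against 222/315; p = 421/630 = 0.668; z = 0.0730/0.0375 = 1.95, which crosses.

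This example was chosen near the limit and shows possibility only.

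**How often.** Both rules were applied to the same simulated trials at 0.65 against 0.76, with final n = 315 per arm and the same number lost in each arm. ICU-discharge rates (control/cilostazol) were 20/20, 40/40, 50/50, 20/31 and 50/61%. About 45% of trials reach the final look.

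| Loss | Opposite conclusions, all trials | Among trials reaching the final look |
|---|---|---|
| 2% | 1.5-2% | 3-4% |
| 5% | 3-4% | 7-9% |
| 10% | 5-7% | 11-17% |

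If the number lost varies by chance between arms, disagreement is more frequent: about 5-10% of all trials at 10% loss over the same ICU-discharge rates.

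**Power at 10% loss.** Under 12.6 the expected rates are 0.9 x 0.65 = 0.585 and 0.9 x 0.76 = 0.684, so the difference falls from 11.0 to 9.9 points. Under LOCF with an equal ICU-discharge rate q in both arms, 0.1q is added to each rate and the difference is again 9.9 points. Ranges cover fixed and random loss counts.

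| Handling of the 10% lost | Power |
|---|---|
| Removed | 0.80 |
| Non-responder | 0.73-0.75 |
| LOCF, equal ICU-discharge rates | 0.74-0.76 |
| LOCF, full 11-point effect at ICU discharge (20/31 to 65/76%) | 0.80-0.82 |

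If lost patients are also scored as non-responders at the interims, power at 10% loss is 0.69.

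**Unequal loss, no true effect (0.65 in both arms), 12% of control and 8% of cilostazol lost.**
- Non-responder: expected 0.88 x 0.65 = 0.572 against 0.92 x 0.65 = 0.598; one-sided type I error about 0.06.
- LOCF at an ICU-discharge rate of 20%: 0.572 + 0.12 x 0.20 = 0.596 against 0.598 + 0.08 x 0.20 = 0.614. Type I error is about 0.05, falling to about 0.03 at a rate of 50%.

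**The case against.** The strongest reply is that 12.6 is one stray sentence. Four places give LOCF and 5.2 collects the value for it, so a careful analyst would use LOCF and nothing would change. That shows which sentence to amend. It does not remove the sentence, which refers explicitly to the main analysis of the primary criterion.

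It is also fair that the effect is limited. Only lost patients with an ICU-discharge mRS of 0-2 change category, the 11-17% applies only to trials that reach the final look at the drop-out ceiling, and the planned analysis is an adjusted logistic regression rather than the pooled z used here. These points stand and are reflected in the figures.

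A reader might infer more than the documents support:
- *That 12.6 alone costs power or inflates error, so LOCF is safe.* With equal ICU-discharge rates LOCF loses nearly as much power, and under unequal loss it also inflates type I error when the ICU-discharge rate lies below the 6-month rate. Nothing in the protocol shows that the treatment effect is already present at ICU discharge.
- *That removing patients who resign breaks the ITT analysis.* Resignation is not defined. If it means withdrawn consent, 5.8.1.2 largely explains the removal and only the wording is out of step.
- *That "A 10% rate of non evaluable patients is foreseen" is a different allowance from the drop-out rate in 12.5 and 5.8.3.* The same 10% can be meant, and 284 of 315 fits it.
- *That the worst-case sensitivity analysis in 12.1 is a further conflict with 12.6.* Worst case is not defined there, so it need not be the rule of 12.6.

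**Conclusion.** The contradiction stands and should be corrected: two different rules are fixed for the primary analysis of the same patients. On the stated assumptions, with equal numbers lost in each arm, the rules lead to opposite final conclusions in about 1.5-2%, 3-4% and 5-7% of all trials at 2, 5 and 10% loss. The loss rates and ICU-discharge rates are assumptions; 10% is the protocol's own drop-out ceiling.

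The power and type I error figures do not favour one rule decisively. The 0.80 at 315 per arm holds if the 10% are removed from the analysis, which neither rule does for patients lost to follow-up. The case for LOCF as the single rule is consistency with the rest of the protocol and with the data collected, not protection of power. The resignation wording is a minor point.

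**What to change.** 1. State one primary rule, identically, in 12.1, 12.2.1, 12.2.2, 12.3 and 12.6. The smallest change is to amend the 12.6 sentence to the rule of 12.1: ICU-discharge mRS carried forward, non-responder only if no mRS is recorded.
2. In the 12.3 table, label multiple imputation as a sensitivity analysis, as 12.2.1 does. Keep non-responder scoring, multiple imputation and complete-case analysis as sensitivity analyses.
3. Whichever rule is kept, say in 12.5 that 0.80 power at 315 per arm assumes the 10% are removed, and give the power under the chosen rule with its loss-rate assumption. For LOCF, also state the assumed ICU-discharge rates.
4. Wording only: limit removal to patients whose data may not be used under 5.8.1.2, report their number by arm, and align the all-randomised wording of the ITT population and the primary estimand.

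The cost is a few sentences. No extra data are needed, since the ICU-discharge mRS is already collected, and resolving the contradiction does not itself require more patients. If the change counts as a substantial modification, 14.9 requires sponsor approval, then a favourable ethics committee opinion and ANSM authorisation. It is best settled before the first interim analysis.

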2.2 Description of knowledge relating to the pathology in question

The incidence rate of subarachnoid hemorrhage (SAH) is approximately 10 per 100,000, among which 85% are caused by a ruptured aneurysm. It accounts for about 5% of all strokes. The mortality rate is 30-50% and delayed cerebral ischemia (DCI) affects about 30% of SAH survivors; the risk of DCI is correlated with the Fisher radiologic score and the World Federation of Neurosurgeons score and contributes to poor outcome, long-term disability and cognitive impairment⁷. The DCI mainly occurs between the 4th and the 10th day after SAH^{8,9}.

To date, only administration of nimodipine, as a preventive strategy of DCI, has been shown to improve long-term neurological outcome^{10,11}. It is therefore widely used, although its efficacy is limited. Its mechanisms of action, as a calcium antagonist, include vasodilatation and antifibrinolytic effect.

Data on curative treatment of vasospasm and DCI shows weak evidence and contradictory results, whether pharmacological or intra-arterial interventions. Therefore, management of these complications differs among intensive care units. However, it always includes close monitoring of clinical deterioration; when it occurs, hypertension therapy, intra-arterial dilatation and sometimes adjuvant therapy such as milrinone are used. If sedation is needed making clinical examination not reliable, monitoring of vasospasm with using transcranial Dopplers, electroencephalographic recordings and perfusion CTscans are performed, although the clinical consequences of a radiological vasospasm, when found, is often a matter of debate.

Despite advances in treatment and care protocols, the mortality and morbidity rate of SAH remains high: up to 40% patients of these adults are unable to return to work and even fewer are able to return to their previous occupations because of neurological impairment¹. Therefore, prevention of DCI remains a major priority.

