4.1.2 Secondary assessment criteria

The main pitfall of the modified Rankin Scale is the overrating of patients that develop cognitive impairment. We thus chose to assess separately cognitive impairment with using specific scales, including the MOCA, ADL and IADL. The SAHOT (SAH-outcome tool) will be finally assessed, as it has been recently developed and validated but not yet commonly used as the mRS¹⁸.

1. SAHOT score (Appendix 2)
2. MOCA score at 6 months (Appendix 3)
3. Return to work at 6 months
4. Activities of Daily Living (ADL) at 6 months (Appendix 4)
5. Instrumental Activities of Daily Living (IADL) at 6 months (Appendix 5)

Other generic morbidity criterion will be used.

6. Length of Intensive Care Unit (ICU) stay
7. Length of hospital stay
8. 28-day mortality

We will also assess the occurrence of cerebral vasospasm, delayed cerebral ischemia and new cerebral infarction as they represent potential confounding factors. Of note cerebral vasospasm diagnosis will be left to the discretion of physician as the strategy to undergo arterial MR/CT scan or DSA differs widely across centres but interpretation of these exams will be requested to be standardized in all participating centres. As aforementioned, New cerebral infarcts will be considered when detected on the CT scan or MRI performed with 6 weeks, (or on the latest CT scan or MRI performed before death within 6 weeks, or at autopsy), but not present on the earlier CT or MRI scan performed between 24 and 48 h after early aneurysm occlusion and not ascribable to other causes

9. Occurrence of DCI during the ICU stay

DCI will be defined as the occurrence of

- Focal neurological deficit (such as hemiparesis, aphasia, apraxia, hemianopia, or neglect), or
- Decrease of at least 2 points on the Glasgow Coma Scale (either on the total score or on one of its components [eye, motor on either side, verbal]).

➤ for at least 1 hour,
 ➤ not apparent immediately after aneurysm occlusion, and
 ➤ cannot be attributed to other causes by means of clinical assessment, CT or MRI scanning of the brain, and appropriate laboratory studies

10. Occurrence of cerebral vasospasm on a brain imaging on digitally substracted angiography (DSA) or Magnetic resonance/computed tomography angiogram (MR/CTA) performed upon clinical signs of delayed cerebral ischemia or severe impairment of cerebral blood velocity in transcranial doppler

Cerebral Vasospasm diagnosis will be defined upon DSA or MR/CTA.

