10.3.3 Specific features of the protocol

All serious and non-serious adverse events must be reported in the CRF.

10.3.3.1 Serious adverse events that do not require the investigator to immediately notify the sponsor

These serious adverse events are only recorded in the "adverse event" section of the case report form.

- **Normal and natural evolution of the pathology:**

Normal and natural evolution of aneurismal SAH is quite variable:

- Even without initial neurological deficit, patients are closely monitored after securisation of the aneurism because of the risk of DCI, vasospasm, hydrocephalus, rebleeding, or any other unspecific complication. Patients in worse neurological condition can be initially intubated; the duration of mechanical ventilation dependst on the subsequent neurological improvement and intercurrent ICU complications.
- Securisation of the aneurism can be performed with endovascular coiling or surgical clipping and lead to ischemic stroke

- Death occurs in approximately 30% of all cases.
- DCI can occur from day 4 until the 21th day after SAH. This risk peaks about the 10th day. DCI can require hypertension therapy and infusion of vasopressor, adjunctive pharmacological treatment, notably milrinone, and endovascular treatment of vasospasm can be requested, but in a centre-dependant way
- Other organ failure might occur as patients might require prolonged ventilatory support and developed ICU related complications, such as nosocomial infection.
- Initial hydrocephalus can worsen the neurological status; it can occur from the first to 15th day. It can require an external ventricular drain. The drain can often be weaned during hospitalisation but if not, internal ventricular drainage can be implanted. It is associated with a risk of nosocomial menigitis.
- When the risk of DCI or other neurological complication is considered low enough, the patient is transferred to the ward until the patient is discharged from the hospital to either the patient's home or a rehabilitation centre.
- **Adverse events likely to be associated with the treatments prescribed as part of the patient's care during the monitoring of the research**

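### The imputation rule for variables other than the primary endpoint presets a centre (mean severity at inclusion) and a spread (placebo intra-patient variability) that cannot be applied to the 6-month functional scores, and it does not keep deaths out of the imputation.

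*Protocol*

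**What the plan says.** Under its missing-data heading, protocol section 12.1 first deals with the primary endpoint: the last recorded mRS is carried forward, and a patient with none recorded counts as a non-responder. It then sets one rule for everything else: "For all other variables, in case of a significant proportion of missing data (>10% of subjects"). When that threshold is passed, a sensitivity analysis by multiple imputation with chained equations (MICE) is to be run on a principle described as conservative. Its centre is set by "using the mean severity at inclusion as the central position parameter". The spread of the imputed values is to come from "an estimate of the intra-patient variability in the placebo group as the dispersion parameter".

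The section adds two qualifications. The first is on status: "Sensitivity analysis based on imputed data will be considered secondary". The second is a deferral: "Further details on the treatment of missing data will be provided in the SAP".

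The variables most exposed are the functional scores in section 4.1.2, for example "MOCA score at 6 months (Appendix 3"), with SAHOT, ADL and IADL. Sections 5.3, 8.1 and 8.2 place them at the 6-month visit. The inclusion-visit list in section 5.1 contains none of them.

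Sections 12.2 and 12.3 say how death is handled, but only for the mRS. On mortality, section 2.2 gives a range in per cent ("The mortality rate is 30-50") and section 10.3.3.1 says "Death occurs in approximately 30% of all cases". Section 12.5 notes that patients with early death and those without surgery are not enrolled. It gives no mortality for those who are.

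**The concern.** The clause is a stated rule, not an open item. It names the quantity on which imputed values are centred and the quantity that sets their spread, and neither exists on the scale of the scores to be imputed. A statistician who follows the text obtains meaningless values. One who writes a sound SAP has to contradict the protocol.

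The second issue is death. The rule covers all other variables, makes no exception for patients who died, and sits in a plan whose efficacy analyses all use every randomised participant. Nothing in the text stops a cognition or daily-living score being imputed for a patient who cannot have one. At stake is the interpretability of the sensitivity analyses for the functional secondary endpoints, which the protocol includes because the mRS can overrate patients with cognitive impairment.

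**Working it through.** **1. Scale and direction.** The candidate centres and the targets, as the protocol defines them:

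| Quantity | Range or coding | Worse direction | Source |
|---|---|---|---|
| Fisher grade | 1 to 4 | higher | Appendix 9 |
| MoCA | out of 30, normal at 26 or more | lower | Appendix 3 |
| ADL | six items, each 0, ½ or 1, so 0 to 6 | lower | Appendix 4 |
| IADL | four items coded 0 or 1, so 0 to 4 | higher | Appendix 5 |
| SAHOT | graded change from before the bleed, item by item | more change | Appendix 2 |

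A mean Fisher grade must lie between 1 and 4. Used as the centre for MoCA, it would put imputed values at 1 to 4 out of 30. Used for ADL, it would fall in range by accident and mean nothing. The scores also run in opposite directions, so one common centre cannot be conservative for all of them.

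Severity at inclusion is not a single measure either. Section 4.2.4 stratifies on Fisher grade, the primary estimand in section 12.2.1 names GCS, and section 5.1 also collects WFNS.

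**2. Spread.** With k_i measurements on patient i, pooled intra-patient variance is Σ_i Σ_j (y_ij − ȳ_i)² / Σ_i (k_i − 1). For a score planned once, k_i = 1 for every patient, so the expression is 0/0. It cannot be estimated in the placebo group or anywhere else.

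**3. Method.** Chained equations impute each incomplete variable by drawing from a model fitted to the others. Centre and spread come from that fit, so supplying them in advance describes a different procedure from the one named.

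**4. When the 10% threshold is passed.** Inputs from section 12.5: 630 patients, from 284 per arm and 10% drop-out. Check: 284/0.9 = 315.6 per arm, against the plan's 315, which is close enough here. The threshold is strict: 10% of 630 is 63, so 64 patients without a score are needed.

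Mortality m among enrolled patients is not in the protocol; 5% to 30% is an assumed range. The chance that deaths alone reach 64 is the binomial tail P(X ≥ 64) with n = 630:

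| Assumed m | Chance deaths alone pass the threshold |
|---|---|
| 5% | below 0.01% |
| 8% | 3% |
| 10% | 47% |
| 12% | 93% |
| 15% or more | above 99.9% |

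For context, the planning rates give 315 × 0.35 + 315 × 0.24 ≈ 186 unfavourable outcomes. Sixty-four deaths would be 64/186, about a third of them.

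Now let a share d of survivors also lack the score. The missing share is m + (1 − m)d, and deaths make up m / [m + (1 − m)d] of the gaps. With d = 10% (an assumption, borrowed from the planned drop-out rate):

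- m = 5%: 0.05 + 0.95 × 0.10 = 14.5% missing, of which deaths are 34%.
- m = 15%: 0.15 + 0.85 × 0.10 = 23.5% missing, of which deaths are 64%.
- m = 30%: 0.30 + 0.70 × 0.10 = 37% missing, of which deaths are 81%.

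Deaths become the majority of the gaps when m exceeds 0.10 × (1 − m), that is, above 0.10/1.10 ≈ 9.1%. At this d, the expected missing share exceeds 10% at any mortality above zero.

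**The case against.** The best defence is that section 12.1 leaves further detail to the SAP and calls the imputed analysis secondary. The deferral covers what is left unsaid, such as predictors, number of imputations and software. It does not repair a centre and spread that are already stated. The point about limited consequence stands in full.

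A second defence is that the rule's scope goes beyond the functional scores. Some items are recorded daily to day 28, where intra-patient variability can exist, and length of stay is collected in hospital and unlikely to be 10% missing. That also stands, which is why the point is confined to the scores planned once, at 6 months.

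On death, a reader might infer that the plan will impute scores for the dead and that deaths will be the main reason the threshold is passed. The documents do not support that:

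- The protocol never says that death counts as missing for these scores.
- Section 12.6 does group death with loss to follow-up, but in a sentence about the primary criterion. Sections 12.2 and 12.3 treat the two as separate intercurrent events.
- The cited 30% and 30-50% describe the disease in general, while section 12.5 says early deaths are not enrolled.
- Even a third of 30% is 63 of 630, which does not exceed 10%.
- At 5% mortality with 10% loss among survivors, deaths are a minority of the gaps.

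What remains is that the wording does not exclude imputing for the dead.

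**Conclusion.** The centre-and-spread clause is wrong as written for MoCA, SAHOT, ADL and IADL. That conclusion rests on the protocol's own scales and visit schedule and needs no assumption about event rates.

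The gap on death is real but narrower: the rule permits imputing these scores for patients who died; it does not require it. How often this would matter depends on mortality among enrolled patients, which cannot be taken from the document. Over the assumed 5% to 30%, the chance that deaths alone set off the rule runs from negligible to near certain, turning at about 10%.

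The effect is limited to conditional sensitivity analyses of secondary endpoints. The primary mRS analysis, its own sensitivity analyses, the interim looks and the sample size are untouched. This should be corrected, but it does not threaten the trial's main conclusion.

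**What to change.** In protocol section 12.1, delete the clause that sets the centre and the dispersion. Replace it with standard multiple imputation by chained equations, using arm, centre, age, a named severity grade, ICU-discharge mRS and the other 6-month scores as predictors, restricted to patients alive at 6 months. Section 5.2 already plans the ICU-discharge mRS, but ties it to loss to follow-up; the text should make clear that it is recorded for every patient.

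State separately, for each 6-month score, how death is handled. Giving deaths the worst rank would match the composite strategy used for the mRS. Analysing survivors with mortality reported alongside is another accepted option. The choice is a trade-off, but it should be made before unblinding.

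The faulty sentence is in the protocol, so correcting the SAP alone would leave the two documents in conflict. The cost is a wording change in the protocol, matching SAP text and some programming. If the ICU-discharge mRS is recorded for all patients, no new data are needed.
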